3.4.3. Planned Doses and Safety Coverage

Five (5) dose levels are planned for the study: 5 mg, 10 mg, 25 mg, 50 mg, and 75 mg.

3.4.3.1. Starting Dose

The starting dose of 5 mg is justified based the maximum recommended safe starting dose (MRSD) method as outline by the FDA.

The FDA guidance suggests calculating a human equivalent dose (HED), based on the NOAEL in the most sensitive or most relevant preclinical species, using scaling factors that are based on differences in body surface area between species. The HED is converted to an MRSD in humans by dividing by a safety factor. The safety factor may be adjusted depending on the pharmacology, toxicology, and preclinical pharmacokinetics of the drug, or previous experience with compounds in the same pharmacologic/structural class. Using the 4-week dog study safety information (NOAEL at 50 mg/kg), the HED was estimated to be 28 mg/kg. Using a safety factor of 100, the estimated MRSD in humans would be 17 mg for a 60 kg human.

The planned doses and the predicted exposure compared to the 4-week dog study NOAEL ($C_{\max} = 7.73 \mu\text{g/mL}$, AUC 111 $\mu\text{g}\cdot\text{h/mL}$ at 50 mg/kg) are presented in [Table 5](#). The estimated human dose that would result in an AUC exposure equivalent to the 4-week dog study NOAEL exposure is 547 mg. Using a safety factor of 100, the starting dose would be ~5.5 mg. As stated above, the MABEL dose may be 7-21 mg. To be conservative, a dose of 5 mg was chosen as the starting dose.

The GSK3008356 starting dose of 5 mg in humans is 0.083 mg/kg based on a 60 kg body weight. This is ~600-fold lower than the dog NOAEL dose (50 mg/kg). The predicted human exposure after a single 5 mg dose is ~122-fold below the C_{\max} and ~109-fold below the AUC at the dog NOAEL ([Table 5](#)).

Planned Doses and Safety Cover

Plasma GSK3008356 concentrations will be determined after each dose cohort and the AUC and C_{\max} will be estimated. The dose for the next cohort will be determined by estimating the predicted exposure based on the observed exposure in the preceding cohort(s). Dose escalation will not exceed the NOAEL exposure in the 4-week dog study.

Table 5 Predicted, Human C_{max}, C₁₂, C₂₄, and AUC(0-∞) Observed and Additional Predicted Human Exposures Following Single Oral Administration of GSK3008356

Proposed dose		Predicted C _{max}	Fold-cover for C _{max}	Predicted C ₁₂	Predicted C ₂₄	Predicted AUC(0-∞)	Fold-cover for AUC
(mg)	(mg/kg) ¹	(ng/mL)	Dog ²	(ng/mL)	(ng/mL)	(ng.h/mL)	Dog ²
5	0.083	63.25	122	26.35	14.55	1015	109
10	0.167	126.5	61	52.70	29.1	2030	55
25	0.417	316.25	24	131.75	72.75	5075	22
50	0.833	632.5	12	263.50	145.5	10150	11
75	1.250	948.75	8	395.25	218.25	15225	7
Actual dose		C _{max}	Fold-cover for C _{max}			Observed AUC(0-∞)	Fold-cover for AUC
(mg)	(mg/kg) ¹	(ng/mL)	Dog ²			(ng.h/mL)	Dog ²
5	0.083	92	84			191	581
10	0.167	191	40			314	353
30	0.500	458.5	17			841	132
75	1.250	890.9	9			1963	57
200	3.333	1865.3	4			5488	20
Additional Predicted doses		Predicted C _{max}	Fold-cover for C _{max}			Predicted AUC(0-∞)	Fold-cover for AUC
(mg)	(mg/kg) ¹	(ng/mL)	Dog ²			(ng.h/mL)	Dog ²
125	2.08	1290	6.0			3620	30.7
250 125q4 x2	4.17	1500	5.2			7236	15.3
250 125q16 x2	4.17	1300	5.9			7115	15.6
200 evening	3.33	2070	3.7			5797	19.1
90 10q1h x 9	1.50	300	25.8			2601	42.7
45 5q1h x 9	0.75	150	51.5			1297	85.6
180 20q1h x 9	3.00	600	12.9			5201	21.3

1. Based on 60 kg human body weight

2. Based on the 4-week dog study, 50 mg/kg/day dose, week 4 average C_{max} (7.73 µg/mL) and AUC(0-t) (111 µg.h/mL)

Observed Doses, Additional Planned Doses, and Safety Cover

The actual doses administered and observed exposures relative to the dog NOAEL are found in [Table 5](#). The highest dose administered (200 mg) had a 4-fold and 20-fold safety coverage to the dog NOAEL Cmax and AUC, respectively.

The expected exposures for the additional Part 1 cohorts will be at or below those observed in the Part 1 cohorts dosed to date ([Table 5](#)).

The proposed doses of GSK3008356 may be adjusted, as appropriate, based on the safety, tolerability, and pharmacokinetic data obtained in preceding cohorts.

3.5. Benefit:Risk Assessment

Summaries of findings from non-clinical studies conducted with GSK3008356 can be found in the [IB](#). The current study, 204856, represents the first administration of GSK3008356 to healthy subjects. Considerations for safety monitoring are derived primarily from non-clinical data. The following section ([Section 3.5.1](#)) outlines the risk assessment and mitigation strategy for this protocol.

3.5.1. Risk Assessment

Potential Risk of Clinical Significance and Summary of Data/Rationale for Risk	Impact on eligibility criteria	Mitigation Strategy
Investigational Product (IP) [e.g., GSK3008256]		

Hepatic Effects
 
Oral 7d repeat dose dog study: Minimal to mild, focal hepatocellular degeneration/necrosis was observed (minimal in one female given 50 mg/kg/day; minimal to mild in the male and female given 200 mg/kg/day). Minimal mixed inflammatory cell infiltrates within liver sinusoids noted for the female given 200 mg/kg/day. Clinical pathology findings included increases in alanine aminotransferase (ALT) (up to 1.96X baseline), increases in aspartate aminotransferase (AST) (up to 1.76X baseline), increased glutamate dehydrogenase (GLDH) (to 3.8X baseline) at all dose levels. Increased total bile acid concentrations (to 3.2X baseline) and decreased plasma albumin and total protein concentrations (to 0.90X baseline) were noted at various testing intervals for dogs given 50 or 200 mg/kg/day. These changes may be related to hepatocellular injury and/or associated with reduced food consumption.
 
Oral 28d and 13 week repeat dose dog studies: Increases ALT were noted for males and females given 2, 5 and 50 mg/kg/day at Week 1 (ranging from 1.88X to 2.5X baseline). By Week 4, increases were 1.72X to 2.2X baseline values. The ALT increases were not progressive with continued dosing. There were no correlative liver histopathology findings. Similar increases in ALT (up to 2.71X baseline) and AST (up to 1.57X) were observed in the 13 week study (evaluating doses up to 60 mg/kg/day) and were reversible following a 4-week off-treatment period.
	
Exclusion criterion #1: ALT and bilirubin > 1.5xULN (isolated bilirubin >1.5xULN is acceptable if bilirubin is fractionated and direct bilirubin <35%).
 
Exclusion criterion #2: Current or chronic history of liver disease, or known hepatic or biliary abnormalities (with the exception of Gilbert's syndrome or asymptomatic gallstones).
 
Exclusion criterion #6 History of regular alcohol consumption within 6 months of the study.
 
Exclusion criterion #10: A positive pre-study Hepatitis B surface antigen or positive Hepatitis C antibody result within 3 months of screening.
	
Sentinel dosing – staggered dosing in 2 subjects in Part 1 Cohort 1 prior to enrolment of the remainder of Cohort 1. LFT evaluation planned at baseline, day 2, day 4, day 7, day 14, day 21, day 28, and also as indicated.
 
Exclusion criteria as noted in column 2.
 
Stopping criterion of ALT ≥3xULN with no rechallenge of drug product.


Potential Risk of Clinical Significance and Summary of Data/Rationale for Risk	Impact on eligibility criteria	Mitigation Strategy

Oral 7d and 28 repeat dose rat study: No hepatic related findings.
 
Oral 13 week repeat dose rat study: Increased liver weights (to 1.2X mean control) were observed in female rats given 1000 mg/kg/day with no clinical pathology or microscopic correlates.
 
HepatoTaq: No significant findings.
		

Gastrointestinal Tolerability
 
Oral 7d, 28d, and 13 week repeat dose dog studies: In the 28d study, excessive salivation was observed for males given ≥ 2 mg/kg/day. Dose-related effects on body weight (decreased body weight gain or body weight loss) and/or reduced food consumption were observed in all studies. Increased frequency of fecal abnormalities (unformed/ stool/mucous and/or watery) were observed in the 13 week study.
 
Oral 7d, 28d, and 13 week repeat dose rat studies: Non-dose related decreases in mean body weight gain for rats were observed in the 7day study. No effects on body weight were noted in the 28 day and 13-week rat studies.
 
Scientific Literature: Clinical DGAT1 inhibition may result in dose limiting nausea, vomiting and, watery (non-malabsorption) diarrhea which stopped upon discontinuation of dosing. (Denison 2014; Meyers 2015).
	
Exclusion criterion #4: Current or chronic history of gastrointestinal illness or conditions interfering with normal gastrointestinal anatomy or motility. Examples include gastrointestinal bypass surgery, cholecystectomy, partial or total gastrectomy, small bowel resection, vagotomy, malabsorption, Crohn's disease, ulcerative colitis, IBS, or celiac sprue.
	
Diarrhea scale (Bristol Stool Form Scale) and frequency of stool (Section 6.5.2).
 
Subject may be withdrawn at any time at the discretion of the investigator for safety.

Potential Risk of Clinical Significance and Summary of Data/Rationale for Risk	Impact on eligibility criteria	Mitigation Strategy

Dermal Effects
 
Oral 7d, 28d, and 13 week repeat dose dog studies: Dose-related, minimal to mild atrophy of the sebaceous glands was observed and was considered to be related to pharmacology. Finding was reversible in the 13 week study following a 4-week off-dose period.
 
Oral 7d, 28d, and 13 week repeat dose rat studies: No dermal-related findings.
 
Scientific Literature: DGAT1 inhibition may result in sebaceous gland atrophy and alopecia as observed in animal studies (Floettmann 2015), but similar effects have not been reported in clinical trials to date.
	None	Subject may be withdrawn at any time at the discretion of the investigator for safety.

Potential Risk of Clinical Significance and Summary of Data/Rationale for Risk	Impact on eligibility criteria	Mitigation Strategy

Testicular Effects
 
Oral 7d and 28d repeat dose dog study: No effects in testes or epididymides observed at doses up to 200 mg/kg/day for 7d and up to 50 mg/kg/day for 28d.
 
Oral 7d, 28d and 13w repeat dose rat study: No effects in testes or epididymides observed at doses up to 300 mg/kg/day for 7d and 28d and up to 1000 mg/kg/day for 13w.
 
Oral 13w repeat dose dog study: Minimal to mild degeneration of the testicular seminiferous tubule epithelium with secondary changes within the epididymides (luminal germ cell debris and/or reduced sperm) was observed in terminal dogs given ≥ 30 mg/kg/day.
 
Following the end of the 4-week off-dose period, testicular degeneration was still present in dogs given 60 mg/kg/day and is not unexpected given the long spermatogenic cycle in dogs (typically 90 days).
	None	
While there is no impact on the study NOAEL, dose regimen selection will be based regimens which will result in human exposure below the oral 13w repeat dose dog testicular observation NOAEL exposure of C_{max} (0.642 $\mu\text{g/mL}$) and AUC(0-t) (5.49 $\mu\text{g.h/mL}$).
 
Subject may be withdrawn at any time at the discretion of the investigator for safety.

Potential Risk of Clinical Significance and Summary of Data/Rationale for Risk	Impact on eligibility criteria	Mitigation Strategy

Cardiovascular Effects
 
Single dose cardiovascular rat and dog studies: In rats, transient increases in heart rate (17%) and blood pressure (18%) were observed at 100 mg/kg but not at 30 and 300 mg/kg. The increases in both heart rate and blood pressure produced a transient increase in rate-pressure-product (RPP; an index of cardiac workload; 37%). Because similar changes were not observed at the highest evaluated dose of 300 mg/kg, a clear relationship to GSK3008356 administration was not established. No acute effects on cardiovascular function were noted in dogs.
 
Oral 28d and 13 week dog studies: No cardiovascular-related findings (ECG assessments).
 
Rabbit left ventricular wedge assay: No effects on QT interval, transmural dispersion of repolarization, QRS duration or contractility (concentrations of up to 10 μM).
 
hERG: IC₂₅ value was estimated to be 85.7 μM (31.49 μg/mL). Insufficient inhibition of hERG occurred to allow for the reliable estimation of an IC₅₀ value. The estimated IC₂₅ value is >150X greater than the estimated free C_{max} in humans at the maximum predicted clinical efficacious dose of 43 mg.
 
Based on the low magnitude and transient nature of the heart rate and blood pressure increases noted in rats and the low risk for QT prolongation (based on in vitro findings), the risk for CV effects in humans is considered low.
	
Exclusion criterion #3: QTcF < 450 msec.
	
Monitoring via telemetry (day 1), 12-lead ECG, and vital signs monitoring.
 
Stopping Criteria (Section 4.5.2): QTcF > 500 msec QTc change from baseline > 60 msec.

Potential Risk of Clinical Significance and Summary of Data/Rationale for Risk	Impact on eligibility criteria	Mitigation Strategy
Study Procedures		

Skin Biopsy
 
Complications of punch skin biopsy are uncommon but may include bleeding, infection, and scarring.
 
Bleeding and infection risk are very uncommon with underlying disease conditions (hemophilia, diabetes, older age, and immunosuppression) slightly increasing the risk.
 
Scarring risk is increased in individuals with a history of scarring.
	
Exclusion criterion #5:
 
History of risk for or actual experience of complications from skin biopsy including excess bleeding, infection, or scarring/keloid formation.
	
Observation of the subject while in the clinical unit and at follow-up after discharge from the unit.
 
Subject may be withdrawn at any time at the discretion of the investigator for safety.

3.5.2. Benefit Assessment

As the subjects of this study are healthy subjects they are not expected to receive any direct benefits from the investigation product. The subject may benefit from the general medical data collected through study assessments such as clinical laboratory tests and ECGs. Participation in the study may provide societal benefit through advancing development of new treatments in an area of unmet need.

3.5.3. Overall Benefit:Risk Conclusion

Conducting this clinical trial is reasonable based on the measures taken to minimize risk to subjects participating, balanced against the potential risks identified in associated with GSK3008356 and the potential general benefits outlined above.

4. SELECTION OF STUDY POPULATION AND WITHDRAWAL CRITERIA

Specific information regarding warnings, precautions, contraindications, adverse events, and other pertinent information on the GSK investigational product or other study treatment that may impact subject eligibility is provided in the Investigator's Brochure (IB).

Deviations from inclusion and exclusion criteria are not allowed because they can potentially jeopardize the scientific integrity of the study, regulatory acceptability or subject safety. Therefore, adherence to the criteria as specified in the protocol is essential.

4.1. Inclusion Criteria

A subject will be eligible for inclusion in this study only if all of the following criteria apply:

AGE
1. Between 18 and 65 years of age inclusive, at the time of signing the informed consent.

TYPE OF SUBJECT AND DIAGNOSIS INCLUDING DISEASE SEVERITY
2. For Part 1 and Part 2: Healthy as determined by the investigator or medically qualified designee based on a medical evaluation including medical history, physical examination, laboratory tests and cardiac monitoring.
3. For Part 3: Obese subjects may have chronic disease not specifically excluded and not requiring chronic medication for treatment and are otherwise healthy as determined by the investigator or medically qualified designee based on a medical evaluation including medical history, physical examination, laboratory tests and cardiac monitoring.
A subject with a clinical abnormality or laboratory parameter(s) which is/are not

specifically listed in the inclusion or exclusion criteria, outside the reference range for the population being studied may be included only if the investigator in consultation with the Medical Monitor agree and document that the finding is unlikely to introduce additional risk factors and will not interfere with the study procedures.

WEIGHT

4. Body weight ≥ 50 kg
5. For Part 1 and Part 2 body mass index (BMI) 19 – 25 kg/m² (inclusive)
6. For Part 3 BMI ≥ 30 kg/m²

SEX

7. Males or Females of non-childbearing potential as follows:

Males:

Male subjects with female partners of child bearing potential must comply with the following contraception requirements (Section 4.3) from the time of first dose of study medication until at least five half-lives of study medication after the last dose of study medication.

- a. Vasectomy with documentation of azoospermia.
- b. Male condom plus partner use of one of the contraceptive options below:
 - Contraceptive subdermal implant
 - Intrauterine device or intrauterine system
 - Oral Contraceptive, either combined or progestogen alone [Hatcher 2007]
Injectable progestogen [Hatcher 2007]
 - Contraceptive vaginal ring [Hatcher 2007]
 - Percutaneous contraceptive patches [Hatcher 2007]

Females:

A female subject is eligible to participate if she is not pregnant (as confirmed by a negative serum human chorionic gonadotrophin (hCG) test), not lactating, and the following conditions applies:

- a. Non-reproductive potential defined as:
 - Pre-menopausal females with one of the following:
 - Documented tubal ligation
 - Documented hysteroscopic tubal occlusion procedure with follow-up confirmation of bilateral tubal occlusion
 - Hysterectomy

- Documented Bilateral Oophorectomy
- Postmenopausal defined as 12 months of spontaneous amenorrhea in questionable cases a blood sample with simultaneous follicle stimulating hormone (FSH) > 40 MIU/ml and estradiol < 40 pg/ml (<147 pmol/L) is confirmatory. Females on hormone replacement therapy (HRT) and whose menopausal status is in doubt will not be allowed.

The investigator is responsible for ensuring that subjects understand how to properly use these methods of contraception.

INFORMED CONSENT

8. Capable of giving signed informed consent which includes compliance with the requirements and restrictions listed in the consent form and in this protocol.

4.2. Exclusion Criteria

A subject will not be eligible for inclusion in this study if any of the following criteria apply:

CONCURRENT CONDITIONS/MEDICAL HISTORY (INCLUDES LIVER FUNCTION AND QTc INTERVAL)

1. ALT and bilirubin >1.5xULN (isolated bilirubin >1.5xULN is acceptable if bilirubin is fractionated and direct bilirubin <35%).
2. Current or chronic history of liver disease, or known hepatic or biliary abnormalities (with the exception of Gilbert's syndrome or asymptomatic gallstones)
3. QTcF > 450 msec (Section 4.3)
4. Current or chronic history of gastrointestinal illness or conditions interfering with normal gastrointestinal anatomy or motility. Examples include gastrointestinal bypass surgery, cholecystectomy, partial or total gastrectomy, small bowel resection, vagotomy, malabsorption, Crohn's disease, ulcerative colitis, IBS, or celiac sprue.
5. History of risk for or actual experience of complications from skin biopsy including excess bleeding, infection, or scarring/keloid formation (Part 2 only).

CONCOMITANT MEDICATIONS

6. Use of prescription or non-prescription drugs, including vitamins, herbal and dietary supplements (including St John's Wort) within 7 days (or 14 days if the drug is a potential enzyme inducer) or 5 half-lives (whichever is longer) prior to the first dose of study drug, unless in the opinion of the Investigator and GSK Medical Monitor the medication will not interfere with the study procedures or compromise subject safety. By exception, subject may take acetaminophen (≤ 2 grams/day) up to 48 hours prior to the first dose of study drug.

RELEVANT HABITS

7. Subjects should refrain from consumption of red wine, Seville oranges, grapefruit or grapefruit juice and/or pummelos, exotic citrus fruits, grapefruit hybrids or fruit juices from 7 days prior to the first dose of study medication until after the final dose.
8. History of regular alcohol consumption within 6 months of the study defined as an average weekly intake of >14 standard drinks. One standard drink is equivalent to 10 g of alcohol: 285 ml of beer, 100 ml of wine or 30 ml of 40% alcohol by volume distilled spirits.
9. For Part 1 and Part 2, urinary cotinine levels indicative of smoking or history or regular use of tobacco- or nicotine-containing products within 3 months prior to screening.

CONTRAINDICATIONS

10. History of sensitivity to any of the study medications, or components thereof or a history of drug or other allergy that, in the opinion of the investigator or Medical Monitor, contraindicates their participation.

DIAGNOSTIC ASSESSMENTS AND OTHER CRITERIA

11. Presence of hepatitis B surface antigen (HBsAg), positive hepatitis C antibody test result at screening or within 3 months prior to first dose of study treatment. For potent immunosuppressive agents, subjects with presence of hepatitis B core antibody (HBcAb) should also be excluded.
12. A positive pre-study drug/alcohol screen.
13. A positive test for HIV antibody.
14. Where participation in the study would result in donation of blood or blood products in excess of 750 mL within 90 day period.
15. The subject has participated in a clinical trial and has received an investigational product within the following time period prior to the first dosing day in the current study: 30 days, 5 half-lives or twice the duration of the biological effect of the investigational product (whichever is longer).
16. Exposure to more than four new chemical entities within 12 months prior to the first dosing day.

4.3. Inclusion and Exclusion Criteria Notes

For contraception requirements, the list provided is an all-inclusive list of those methods that meet the following GSK definition of highly effective: having a failure rate of less than 1% per year when used consistently and correctly and, when applicable, in accordance with the product label. For non-product methods (e.g., male sterility), the investigator determines what is consistent and correct use. The GSK definition is based on the definition provided by the International Conference on Harmonization (ICH) [ICH, M3 (R2) 2009].”

4.4. Screening/Baseline/Run-in Failures

Screen failures are defined as subjects who consent to participate in the clinical trial but are never subsequently randomized. In order to ensure transparent reporting of screen failure subjects, meet the Consolidated Standards of Reporting Trials (CONSORT) publishing requirements, and respond to queries from Regulatory authorities, a minimal set of screen failure information is required including Demography, Screen Failure details, Eligibility Criteria, and Serious Adverse Events (SAE) (see Section 6.3.1.4).

4.5. Withdrawal/Stopping Criteria

The following actions must be taken in relation to a subject who fails to attend the clinic for a required study visit:

- The site must attempt to contact the subject and re-schedule the missed visit as soon as possible.
- The site must counsel the subject on the importance of maintaining the assigned visit schedule and ascertain whether or not the subject wishes to and/or should continue in the study.
- In cases where the subject is deemed ‘lost to follow up’, the investigator or designee must make every effort to regain contact with the subject (where possible, 3 telephone calls and if necessary a certified letter to the subject’s last known mailing address or local equivalent methods). These contact attempts should be documented in the subject’s medical record.
- Should the subject continue to be unreachable, only then will he/she be considered to have withdrawn from the study with a primary reason of “Lost to Follow-up”.

A subject may withdraw from study treatment at any time at his/her own request, or may be withdrawn at any time at the discretion of the investigator for safety, behavioural or administrative reasons. If a subject withdraws from the study, he/she may request destruction of any samples taken, and the investigator must document this in the site study records.

[figure not shown]
The reason(s) for not completing the study will be recorded in the case report form (CRF), and the investigator must document, if applicable, the reason (if specified by the subject) for withdrawal of consent. A withdrawn subject may be replaced with another subject who will be assigned to the same treatment randomization.

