3. STUDY DESIGN

3.1. Overall Design

Study 204856 will be a randomized, double-blind (sponsor unblind), placebo controlled trial in three Parts.

1. Part 1, will be a single-dose (SD), dose-rising study in healthy subjects. Subjects will receive GSK3008356 (or matching placebo), as a single dose in each of five sequential cohorts while receiving a standard 30% fat meal. The initial dosing for the first cohort will be staggered so that 2 subjects will be dosed as sentinel subjects. Provided there are no safety concerns, the remainder of the subjects scheduled for the cohort may be dosed.

2. Part 2, will be a 14-day, repeat-dose (RD), dose-rising study in healthy subjects. Subjects will receive GSK3008356 (or matching placebo), as 14 daily doses in each of three sequential cohorts. Day 1 and day 14 dosing for the first cohort will occur while receiving a standard 30% fat meal. The final two cohorts will receive the same morning 30% fat meals, but will explore daily dosing in the evening rather than in the morning.
3. Part 3, will be a 28-day, repeat-dose study in obese subjects. Subjects will receive GSK3008356 (or matching placebo), as 28 daily doses in each of three parallel cohorts. Cohort 1 will evaluate 1 dose strength of GSK3008356 (or matching placebo) administered as morning doses. Cohorts 2 and 3 will evaluate 2 dose strengths (1 per cohort) of GSK3008356 (or matching placebo) administered in the evening.

Please refer to [Figure 1](#) for details.

Figure 1 Study Part Schematic

Part 1 - SD

[figure not shown]
Part 1 – additional cohorts

Part 2 – RD (14d)

Part 3 – RD (28d)

3.1.1. Additional Cohorts for Part 1

Based on emerging PK data, the original planned Part 1 doses were adjusted, per protocol, to 5, 10, 30, 75 and 200 mg (Section 5.3, Figure 1). This was due to a much shorter observed half-life compared to the predicted half-life (1.5-3h observed versus 14.1h predicted).

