3.2. Type and Number of Subjects

Part 1, Single Dose, Healthy Subjects:

Approximately 40 subjects will be enrolled, 8 in each cohort, such that approximately 6-8 subjects complete dosing and critical assessments in each Part 1 Cohort. Additional subjects/cohorts may be enrolled to allow for evaluation of additional dose levels. The six additional cohorts will enrol approximately 48 subjects.

Part 2, 14d Repeat Dose, Healthy Subjects:

Approximately 24 subjects will be enrolled, 8 in each cohort, such that approximately 6-8 subjects complete dosing and critical assessments in each Part 2 Cohort. Additional subjects/cohorts may be enrolled to allow for evaluation of additional dose levels.

Part 3, 28d Repeat Dose, Obese Subjects:

Approximately 30 subjects will be enrolled, 10 in each cohort, such that approximately 6-10 subjects complete dosing and critical assessments in each Part 3 Cohort. Additional subjects/cohorts may be enrolled to allow for evaluation of additional dose levels.

If subjects prematurely discontinue the study, additional replacement subjects may be randomised and assigned to the same treatment sequence at the discretion of the Sponsor in consultation with the investigator.

For Parts 1 and 2, data from prior doses cohorts will be available prior to escalation decisions. Data from Parts 1 and 2 will be available prior to initiation of the three parallel cohorts in Part 3. A dose escalation meeting will be held to review these data and document the decision to proceed as planned or make any alterations in dosing, if indicated (Section 9.8.1).

Subjects in Parts 1 and 2 will be randomized such that 6 subjects receive GSK3008356 and 2 subjects receive matching placebo in each cohort of 8 subjects. Subjects in Part 3 will be randomized such that 8 subjects receive GSK3008356 and 2 subjects receive matching placebo in each cohort of 10 subjects.

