5.4. Blinding

This will be a double blind (sponsor unblind) study and the following will apply.

- The investigator or treating physician may unblind a subject's treatment assignment **only in the case of an emergency** OR in the event of a serious medical condition when knowledge of the study treatment is essential for the appropriate clinical management or welfare of the subject as judged by the investigator.
- Investigators have direct access to the subject's individual study treatment.
- It is preferred (but not required) that the investigator first contacts the Medical Monitor or appropriate GSK study personnel to discuss options **before** unblinding the subject's treatment assignment.
- If GSK personnel are not contacted before the unblinding, the investigator must notify GSK as soon as possible after unblinding, but without revealing the treatment assignment of the unblinded subject, unless that information is important for the safety of subjects currently in the study.
- The date and reason for the unblinding must be fully documented in the CRF

A subject will be withdrawn if the subject's treatment code is unblinded by the investigator or treating physician. The primary reason for discontinuation (the event or condition which led to the unblinding) will be recorded in the CRF.

- GSK's Global Clinical Safety and Pharmacovigilance (GCSP) staff may unblind the treatment assignment for any subject with an SAE. If the SAE requires that an expedited regulatory report be sent to one or more regulatory agencies, a copy of the report, identifying the subject's treatment assignment, may be sent to investigators in accordance with local regulations and/or GSK policy.

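### A subject withdrawn after a code break may be replaced on the same assignment, so the replacement can be assessed by an investigator who already knows the treatment

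*Protocol*

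**What the plan says.** Protocol Section 3.1 describes a "randomized, double-blind (sponsor unblind), placebo controlled trial in three Parts", so the site is meant to be blind. Section 9.7 withholds the randomisation codes from the investigator until the full analysis is complete.

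On unblinding, Section 5.4 limits code breaks to emergencies or serious conditions in which knowing the treatment is essential. It also states "Investigators have direct access to the subject's individual study treatment", makes prior contact with the sponsor preferred but not required, and adds: "A subject will be withdrawn if the subject's treatment code is unblinded by the investigator or treating physician". Separately, the sponsor's safety staff may unblind a subject with an SAE, and a copy of an expedited report, "identifying the subject's treatment assignment, may be sent to investigators in accordance with local regulations and/or GSK policy".

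On replacement, Section 4.5 says "A withdrawn subject may be replaced with another subject who will be assigned to the same treatment randomization". Section 3.2 says "additional replacement subjects may be randomised and assigned to the same treatment sequence at the discretion of the Sponsor in consultation with the investigator". SAP Section 11.7.1 repeats the Section 4.5 sentence. None of the three distinguishes withdrawals by reason.

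**The concern.** Each rule is ordinary alone; the difficulty comes from combining them. Withdrawing a subject whose code is broken limits further assessment under a known treatment. Giving the replacement that same assignment can bring the problem back with a new subject, this time from the first dose.

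The data at stake are primary. Safety and tolerability are the primary objective of every part. Adverse event intensity and causality are investigator judgements (Protocol Section 11.3.5), and the SAP's drug-related event tables rest on the investigator's yes/no answer (SAP Section 7.1.1.4). The Principal Investigator or a designee also sits on the Dose Escalation Committee, whose minimum data set includes adverse event listings (Protocol Section 9.8.1). Placebo is randomised within each cohort so that such judgements can be made blind.

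**Working it through.** There is no plan figure to reproduce: Protocol Section 8.2 bases sample size on feasibility, without a power calculation. The check sets the rules side by side and then sizes the effect.

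**Chain of conditions.** All of these must hold:

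1. A code is broken by the investigator or treating physician. Section 5.4 then requires withdrawal.
2. The sponsor, consulting the investigator, chooses to replace (Sections 3.2 and 4.5). The replacement receives the same assignment.
3. The person assessing the replacement knows the broken code.
4. That person knows whom the replacement stands for.

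Section 3.2 makes condition 4 plausible by involving the investigator in the replacement decision. No section excludes code-broken subjects from replacement, re-randomises the newcomer, masks the link or provides a separate blinded assessor.

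The SAE-report route differs. Unblinding by the sponsor's safety staff does not trigger the Section 5.4 withdrawal rule, so this route matters only if the report reaches the investigator and the subject also leaves the study and is replaced.

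**What the investigator knows.** For a subject randomised in the usual way, the chance of active drug is 6/8 = 75% in Parts 1 and 2, or 8/10 = 80% in Part 3. When all four conditions hold it is 100% or 0%.

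**Share of the data from one such replacement.**

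Inputs:
- Allocation is 6 active to 2 placebo per cohort in Parts 1 and 2, and 8 to 2 in Part 3 (Protocol Section 3.2).
- The Safety population is everyone who received at least one dose (Protocol Section 8.3.1; SAP Section 4), so a withdrawn subject who was dosed stays in beside the replacement.
- Adverse events are summarised with placebo pooled within part (SAP Section 7.1.1.1).
- Part 1 lists eleven cohorts, of which Cohort 9 was cancelled, leaving ten; Part 2 has three (SAP Section 11.5.1).

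Formula: share = 1 / (planned group size + 1).

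| Group | Calculation | Share |
|---|---|---|
| Active, one cohort, Parts 1-2 | 1/(6 + 1) = 1/7 | 14.3% |
| Pooled placebo, Part 1 | 1/(10 × 2 + 1) = 1/21 | 4.8% |
| Pooled placebo, Part 2 | 1/(3 × 2 + 1) = 1/7 | 14.3% |
| Placebo, one cohort unpooled, any part | 1/(2 + 1) = 1/3 | 33.3% |
| Active, one cohort, Part 3 | 1/(8 + 1) = 1/9 | 11.1% |

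The Part 3 row describes the protocol only: SAP Section 2.2 states that Part 3 was not initiated.

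**Whether the SAP would reveal it.** SAP Listing 4 covers subjects whose blind was broken. A replacement's own code need never have been broken, so the replacement need not appear there. Listing 5 gives planned and actual treatments but does not mark replacements.

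**The case against.** The strongest reply is that the conditions will seldom all hold. Code breaks are restricted to emergencies and serious conditions. The breaker may be a treating physician who does not assess the replacement. Replacement is optional, and the sponsor, already unblinded, can decline it. No section says that the site is told whom a newcomer replaces. All of this stands and limits how often the problem can arise. None of it closes the gap, because the documents require no safeguard at any of these steps.

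The consequence is also bounded. No hypothesis is tested, safety is summarised descriptively, and the primary endpoint includes laboratory tests, vital signs and ECGs, which depend less on expectation. Section 5.4 requires the date and reason for unblinding to be recorded in the CRF, which with Listings 4 and 5 gives a starting point for tracing a case.

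A reader might infer more than the documents support:

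- That the investigator always knows the replacement's treatment. This requires conditions 3 and 4, which the documents make possible but do not state.
- That an expedited SAE report has the same effect. It does not itself cause withdrawal.
- That one replacement is 1/6 of the active group or half of placebo. Those fractions drop the withdrawn dosed subject, who remains in the Safety population, and the one-half also ignores pooling of placebo within part.
- That it happened. SAP Section 2.2 reports early withdrawals in Part 2 Cohort 1 but mentions no code break or replacement.

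**Conclusion.** The concern holds in conditional form. Followed as written, Protocol Sections 5.4, 4.5 and 3.2 permit a replacement to be dosed and assessed by an investigator who knows the treatment, and nothing in either document prevents or flags it. The event is likely rare, although the documents give no frequency for code breaks.

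One occurrence would be about 14% of a Part 1 or 2 cohort's active group, about 5% of the pooled Part 1 placebo group, or about 14% of the pooled Part 2 placebo group. These shares assume full enrolment at the planned ratio, no other replacements, and a withdrawn subject who had been dosed. They describe how much of the summary would rest on unblinded assessment; neither the size nor the direction of any resulting bias can be derived from the documents.

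**What to change.** **Protocol Sections 4.5 and 3.2.** State that a subject whose treatment has become known to the investigator, through a code break or a report naming the treatment, is not replaced on that same assignment. If the cohort must be topped up, use a reserve allocation generated with the original schedule and concealed from the site. The rules on emergency unblinding and withdrawal are untouched.

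**SAP.** An allocation rule does not belong in the SAP, which was written after the Part 2 outcomes were known. The SAP should only identify any replacement entered after a disclosed code and flag that subject in the adverse event listings. For the study as conducted, this is the part that can still be acted on.

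**Cost.** One sentence in each of the two protocol sections, a short reserve list and one listing flag. The real downside is balance. Not replacing, or drawing afresh, may leave a cohort one subject off 6:2 (or 8:2), and if the lost subject was on placebo the cohort may have only one completing placebo subject. There is no power calculation to disturb, and Protocol Section 9.8.1 asks for data from at least 4 active subjects for an escalation decision, so losing one of 6 does not by itself block escalation.
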